## **6.5. Assessments for Premature Discontinuation from Study**

If a subject discontinues study dosing (for example, as a result of an AE), every attempt should be made to keep the subject in the study and continue to perform the required study-related follow-up and procedures (see Section 6.6, Criteria for Discontinuation of Study Treatment). If this is not possible or acceptable to the subject or investigator, the subject may be withdrawn from the study.

## **6.6. Criteria for Discontinuation of Study Treatment**

Study medication will be discontinued in the following instances:

- Development of active tuberculosis infection
- Unacceptable toxicity, or toxicity that, in the judgment of the investigator, compromises the ability to continue study-specific procedures or is considered to not be in the subject's best interest
- Lack of efficacy
- Subject request to discontinue for any reason

Study medication may be discontinued in the following instances:

- Intercurrent illness that would, in the judgment of the investigator, affect assessments of clinical status to a significant degree. Following resolution of intercurrent illness, the subject may resume study dosing at the discretion of the investigator.
- Subject noncompliance
- Discontinuation of the study at the request of Gilead, a regulatory agency or an institutional review board or independent ethics committee (IRB/IEC)

## **6.7. End of Study**

End of study is defined as completion of the 96 weeks of treatment and the 30 Day Follow-Up visit. Subjects that enter the post Week 96 extension phase will have the week 96 study visit, then up to 48 weeks on the extension phase and the 30 Day Follow-Up visit.

## **6.8. Post Study Care**

After a subject has completed/terminated their participation in the study, long-term care for the subject will remain the responsibility of their primary treating physician.

## 6.9. Blood Samples

Blood sample collection for the following laboratory analyses:

- Chemistry profile: alkaline phosphatase, AST, ALT, total bilirubin, direct and indirect bilirubin, total protein, albumin, bicarbonate, BUN, calcium, chloride, creatinine, glucose, potassium, sodium (all visits)
- Hematology profile: complete blood count (CBC) with differential and platelet count (all visits)
- CD4+ cell count (all visits)
- Plasma HIV-1 RNA (TaqMan® v2.0) (all visits)
- Hepatitis B virus surface antigen (HBsAg), Hepatitis B virus surface antibody (HBsAb) and Hepatitis B virus core antibody (HBcAb). The following tests will be conducted by the central laboratory if the following criteria are met (Screening visit)
  - If positive HBsAg: reflex testing for plasma HBV DNA, Hepatitis B virus e-antigen (HBeAg) (if negative, reflex Hepatitis B virus e-Antibody [HBeAb]), and quantitative HBsAg
  - If positive HBcAb with negative HBsAg and negative HBsAb: reflex testing for plasma HBV DNA (if positive, reflex HBeAg). If HBeAg is performed and found to be negative, reflex HBeAb
- Hepatitis C virus (HCV Ab) serology (reflex HCV RNA is performed in subjects with positive HCV Ab serology) (Screening Visit)
- Metabolic assessments: Fasting (no food or drink, except water, at least 8 hours prior to blood collection) glucose and lipid panel (total cholesterol, HDL, direct LDL, and triglycerides) (Day 1, Weeks 24, 48 and 96); metabolic assessments will not be collected after Week 96.
- If the subject has not fasted prior to the visit, the visit may proceed, but the subject must return within 72 hours in a fasted state.
- Biomarkers to be analyzed may include but will not be limited to: soluble glycoprotein VI (sGPVI), P-selectin, soluble CD40 ligand, and d-dimer (Day 1, Weeks 4, 12, 24, 48, 60, 72, 84, and 96); Biomarkers will not be collected after Week 96. A portion of the biomarker blood sample obtained at Day 1, Weeks 4, 12, 24, 48, 60, 72, 84, and 96 may be utilized to assess study drug PK. This will be a random sample with the date and time of the subject's last medication dose recorded.

- Inflammation evaluations may include: cystatin-C, IL 6, hs CRP, sCD14, sCD163, sTNF-R1, and Lp-PLA2. Specimens will be collected from all subjects (Day 1, Weeks 4, 12, 24, 48, 60, 72, 84, and 96). Inflammation markers will not be collected after Week 96.
- Plasma storage sample for safety and/or virology testing (all visits)
- Whole blood sample for virology (Screening and Day 1)

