#### **6.4.2. 30 Day Follow-Up Visit**

- For subjects discontinuing study between Day 1 – Week 96

If the subject discontinues study drug and does not continue in the study, the subject will be required to return to the clinic 30 days after the completion of the Early Study Drug Discontinuation Visit for the 30-Day Follow-Up visit.

If the subject discontinues study drug and continues in the study through at least one subsequent visit after the Early Study Drug Discontinuation Visit, the subject will not be required to complete the 30-Day Follow-Up Visit.

If the subject completes the study drug through Week 96 and does not continue participation in the post Week 96 extension phase, the subject will be required to return to the clinic 30 days after the completion of study drug for the 30-Day Follow-Up visit.

- For subjects discontinuing study post Week 96 extension phase

If the subject discontinues study drug before the completion of post Week 96 extension phase, the subject will be required to return to the clinic 30 days after the completion of the Early Study Drug Discontinuation Visit for the 30-Day Follow-Up visit

If the subject continues participation in the extension phase post Week 96, the subject will be required to return to the clinic 30 days after the completion of the extension phase for the 30-Day Follow-Up visit.

For the purpose of scheduling a 30-Day Follow-Up Visit, a  $\pm 6$  days window may be used. The following evaluations are to be completed at the 30-Day Follow-Up Visit:

- Review of AEs and changes in concomitant medications
- Symptom-directed physical examination
- Vital signs measurement, including weight
- Obtain blood and urine samples as described in Sections 6.9 and 6.10

At the 30 Day Follow-Up visit any evaluations showing abnormal results indicating that there is a possible or probable causal relationship with the study drug will be repeated weekly (or as often as deemed prudent by the Investigator) until the abnormality is resolved, returns to baseline, or is otherwise explained.

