**6.12.2. Subjects with HIV-1 RNA  $\geq$  50 copies/mL at Study Drug Discontinuation or at Week 48, Week 72 or Week 96**

Subjects with HIV-1 RNA  $\geq$  50 copies/mL at study drug discontinuation or last visit will be considered virologic failures. Subjects with HIV-1 RNA  $\geq$  50 copies/mL at Weeks 48, 72 or 96 will be asked to return for an unscheduled visit within the visit window for a retest.

Subjects with HIV-1 RNA  $\geq$  200 copies/mL at study drug discontinuation, last visit, or last measurement in the Weeks 48, 72 or 96 window, will also have resistance testing conducted.

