**Appendix 2. Study Procedures Table**

Study Procedure	Screening a	Day 1 b	End of Week c									Post Week 96 extension phase	Early Study Drug Discontinuation (ESDD) d	30-Day Follow-up	
			4	12	24	36	48	60	72	84	96	Every 12 weeks for 48 weeks (until Week 144)			
Informed Consent	X														
Medical History	X														
Concomitant Medications	X	X	X	X	X	X	X	X	X	X	X	X	X	X	X
Adverse Events	X	X	X	X	X	X	X	X	X	X	X	X	X	X	X
Complete Physical Exam e	X	X					X				X			X	
Symptom-Directed Physical Exam			X	X	X	X		X	X	X			X		X
Vital Signs and Weight	X	X	X	X	X	X	X	X	X	X	X	X	X	X	X
Height	X														
12-lead ECG	X						X				X			X	
Urinalysis and Urine Chemistry	X	X	X	X	X	X	X	X	X	X	X	X	X	X	X p
Renal Safety Evaluations – Urine f		X	X	X	X		X	X	X	X	X				
Biomarkers: inflammation, platelet, renal g		X	X	X	X		X	X	X	X	X				
Urine Storage Sample		X	X	X	X	X	X	X	X	X	X	X	X	X	
Chemistry Profile h	X	X	X	X	X	X	X	X	X	X	X	X	X	X	X
Hematology Profile i	X	X	X	X	X	X	X	X	X	X	X	X	X	X	X
CD4+ Cell Count	X	X	X	X	X	X	X	X	X	X	X	X	X	X	
Plasma HIV-1 RNA j	X	X	X	X	X	X	X	X	X	X	X	X	X	X	
HBV and HCV Serologies k	X														
Cystatin-C		X													
Estimated GFR l	X	X	X	X	X	X	X	X	X	X	X	X	X	X	
Whole Blood Sample m	X	X													

[figure not shown]
Study Procedure	Screening a	Day 1 b	End of Week c									Post Week 96 extension phase	Early Study Drug Discontinuation (ESDD) d	30-Day Follow-up
			4	12	24	36	48	60	72	84	96	Every 12 weeks for 48 weeks (until Week 144)		
Metabolic Assessments n		X			X		X				X			
Plasma Storage Sample o		X	X	X	X	X	X	X	X	X	X	X	X	X
Patient reported outcomes: VAS		X	X	X	X	X	X	X	X	X	X		X	
Patient reported outcome: HIVTSQs		X												
Patient reported outcome: HIVTSQ e			X		X		X						X	
Patient reported outcome: EQ-5D		X			X		X							
Patient reported outcome: SF-36		X			X		X							
Patient reported outcome: FACIT-F		X			X		X							
HIV-1 Genotype/Phenotype q							X		X		X		X	
Study Drug Dispensation and Accountability		X	X	X	X	X	X	X	X	X	X	X	X	X r

- a Evaluations to be completed within 30 days prior to Day 1 visit.
- b Subjects will be dispensed study drug at the Day 1 visit; initiation of treatment with the study drug must take place within 24 hours after the Day 1 visit.

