- For baseline, the latest available record on or prior to the first dose date of B/F/TAF study drug will be selected. If there are multiple records with the same collection time or no collection time recorded on the same day, average will be used for the baseline value, except for HIV-1 RNA (see below).
- For postbaseline visits:
 - For CD4+ cell count, and CD4%, the record(s) collected on the latest day in the window will be selected for analysis.
 - For other numeric observations (eg, except HIV-1 RNA, CD4+ cell count, and CD4%), the record(s) collected on the day closest to the nominal day for that visit will be selected. If there are 2 days equidistant from the nominal day, the later day will be selected.
 - For any numeric observations except HIV-1 RNA, if there are multiple records on the selected day, the arithmetic mean will be used.
- For baseline and postbaseline HIV-1 RNA, the latest (considering both collection date and time) record(s) in the window will be selected. If both “HIV RNA Taqman 2.0” and “HIV RNA Repeat” (ie, the HIV-1 RNA result obtained from an additional aliquot of the original sample) are available with the same collection time, the results from the “HIV RNA Repeat” will be selected for analysis purposes; otherwise, if there are multiple “HIV RNA Taqman 2.0” records with the same collection time, the geometric mean will be taken for analysis purposes.

If multiple valid nonmissing categorical observations exist in a window, records will be chosen as follows:

- For baseline, the last available record on or prior to the first dose date of B/F/TAF study drug will be selected. If there are multiple records with the same collection time or no collection time recorded on the same day, the value with the lowest severity will be selected (eg, normal will be selected over abnormal for safety ECG findings).
- For postbaseline visits, the most conservative value within the window will be selected (eg, abnormal will be selected over normal for safety ECG findings).

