6.2.2. Analysis of CD4 Cell Count and CD4%

CD4 cell count and CD4% will be summarized using observed, on-treatment data (ie, data collected up to 1 day after the last dose date of B/F/TAF) for subjects in the FAS.

The changes from baseline in CD4 cell count and CD4% at each visit will be summarized using descriptive statistics based on observed data (ie, missing will be excluded) using the FAS.

The mean and 95% CI of change from baseline in CD4 cell count over time will be plotted using observed data for the FAS.

6.2.3. Analysis of the Proportion of Subjects with HIV-1 RNA < 50 copies/mL by Missing Failure and Missing Excluded Approach

The proportion of subjects with HIV-1 RNA < 50 copies/mL will also be summarized using the following 2 methods for imputing missing HIV-1 RNA values:

- Missing Failure (M F)

In this approach, all missing data will be treated as HIV-1 RNA \geq 50 copies/mL. The denominator for percentages is the number of subjects in the FAS. Data will be summarized through Week 96.

- Missing Excluded (M E)

In this approach, all missing data will be excluded in the computation of the percentages (ie, missing data points will be excluded from both the numerator and denominator in the computation). The denominator for percentages at a visit is the number of subjects in the FAS with non-missing HIV-1 RNA value at that visit.

For both M F and M E analysis, the number and percentage of subjects with HIV-1 RNA in the following categories will be summarized:

- < 50 copies/mL
 - < 20 copies/mL
 - < 20 Not Detectable
 - < 20 Detectable
 - 20 to < 50 copies/mL
- \geq 50 to < 200 copies/mL
- \geq 200 to < 400 copies/mL
- \geq 400 < 1000 copies/mL
- \geq 1000 copies/mL

The 95% CI of the proportion of subjects with HIV-1 RNA < 50 copies/mL will be provided using the Clopper-Pearson Exact method.

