Appendix 1. Study Procedures Table

Study Procedure	Screening ^a	Day 1 ^b	End of Week ^c									Early Study Drug Discontinuation (ESDD) ^d	30-Day Follow-up
			4	12	24	36	48	60	72	84	96		
Informed Consent	X												
Medical History	X												
Concomitant Medications	X	X	X	X	X	X	X	X	X	X	X	X	X
Adverse Events	X	X	X	X	X	X	X	X	X	X	X	X	X
Complete Physical Exam ^e	X	X					X				X		
Symptom Directed Physical Exam			X	X	X	X			X	X	X		X
Vital Signs and Weight	X	X	X	X	X	X	X	X	X	X	X	X	X
Height	X												
12 lead ECG	X						X				X		X
Urinalysis and Urine Chemistry	X	X	X	X	X	X	X	X	X	X	X	X	X ^p
Renal Safety Evaluations Urine ^f		X	X	X	X		X	X	X	X	X		
Biomarkers: inflammation, platelet, renal ^g		X	X	X	X		X	X	X	X	X		
Urine Storage Sample		X	X	X	X	X	X	X	X	X	X	X	
Chemistry Profile ^h	X	X	X	X	X	X	X	X	X	X	X	X	X
Hematology Profile ⁱ	X	X	X	X	X	X	X	X	X	X	X	X	X
CD4+ Cell Count	X	X	X	X	X	X	X	X	X	X	X	X	
Plasma HIV 1 RNA ^j	X	X	X	X	X	X	X	X	X	X	X	X	
HBV and HCV Serologies ^k	X												
Cystatin C		X											
Estimated GFR ^l	X	X	X	X	X	X	X	X	X	X	X	X	

CCI

Study Procedure	Screening ^a	Day 1 ^b	End of Week ^c									Early Study Drug Discontinuation (ESDD) ^d	30-Day Follow-up
			4	12	24	36	48	60	72	84	96		
Whole Blood Sample ^m	X	X											
Metabolic Assessments ⁿ		X			X		X				X		
Plasma Storage Sample ^o		X	X	X	X	X	X	X	X	X	X	X	
Patient reported outcomes: VAS		X	X	X	X	X	X	X	X	X	X	X	
Patient reported outcome: HIVTSQs		X											
Patient reported outcome: HIVTSQ ^c			X		X		X					X	
Patient reported outcome: EQ 5D		X			X		X						
Patient reported outcome: SF 36		X			X		X						
Patient reported outcome: FACIT F		X			X		X						
HIV 1 Genotype/Phenotype ^q							X		X		X	X	
Study Drug Dispensation and Accountability		X	X	X	X	X	X	X	X	X	X	X ^r	

a Evaluations to be completed within 30 days prior to Day 1 visit.

b Subjects will be dispensed study drug at the Day 1 visit; initiation of treatment with the study drug must take place within 24 hours after the Day 1 visit.

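### If HIV-1 RNA is drawn at the 30-Day Follow-Up, as Protocol 6.4.2 and 6.9 order but the procedures tables do not, SAP 3.8.3 can make it the Week 96 value in the Missing=Failure and Missing=Excluded analyses

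*Protocol*

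**What the plan says.** **Whether the sample is drawn.** Protocol 6.9 gives the schedule for each blood test, and its HIV-1 RNA entry reads "Plasma HIV-1 RNA (TaqMan® v2.0) (all visits". CD4+ count carries the same tag. The evaluation list for the 30-Day Follow-Up in 6.4.2 includes "Obtain blood and urine samples as described in Sections 6.9 and 6.10" and does not limit the tests. The HIV-1 RNA and CD4 rows of Protocol Appendix 2 and SAP Appendix 1 are marked from Screening to the early discontinuation visit and blank at the 30-Day Follow-Up. Neither document says whether text or table prevails.

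**When the visit falls.** For a subject who finishes at Week 96, Protocol 6.4.2 states that "the subject will be required to return to the clinic 30 days after the completion of study drug for the 30-Day Follow-Up visit", with a ±6-day allowance. SAP 1.2 says all subjects leave at Week 96 and then have a 30-day follow-up.

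**Which value is used.** SAP Table 3-1 sets the Week 96 window at Day 631–714. Where several HIV-1 RNA records lie in one window, SAP 3.8.3 says "the latest (considering both collection date and time) record(s) in the window will be selected". SAP 6.2.1 (snapshot) and 6.2.2 (CD4) restrict data to one day after the last dose. SAP 6.2.3 has no such restriction. For Missing=Excluded it says only: "The denominator for percentages at a visit is the number of subjects in the FAS with non-missing HIV-1 RNA value at that visit".

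**Virologic failure.** Protocol 6.12.2 says subjects with HIV-1 RNA ≥ 50 "copies/mL at study drug discontinuation or last visit will be considered virologic failures". The definition in 6.12 has no last-visit category.

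**The concern.** A site that follows the protocol text draws HIV-1 RNA about 30 days after study drug has ended; a site that follows the table does not. Where the value exists, a programmer applying SAP 3.8.3 literally would replace the completer's Week 96 on-drug result with it in the two analyses of SAP 6.2.3. SAP 6.1.2 names both, at Week 96, among its secondary efficacy endpoints.

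Those tables would then describe roughly Week 100, off study drug, while the snapshot beside them describes Week 96 on drug. A gap between them could be put down to missing-data handling when part of it is timing. If sites differ in which instruction they follow, the result also depends on site.

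The last-visit wording of Protocol 6.12.2 is a related loose end. Read with 6.9, it could label a completer a virologic failure on a post-drug value, a case that 6.12 does not list.

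**Working it through.** **Inputs**

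- Nominal days 588 (Week 84) and 672 (Week 96), window 631–714: SAP Table 3-1.
- Week 96 visit ±6 days by default, ±6 weeks if the sponsor notifies: Protocol 6.3.1.
- Follow-up 30 ± 6 days after completing study drug: Protocol 6.4.2. I assume the last dose is on the day of the Week 96 visit.
- 86 subjects in the Safety Analysis Set: SAP Appendix 7 mock-up. The Full Analysis Set count is not given.

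**1. Reproduce the window.** Lower limit = (588 + 672)/2 + 1 = 631. Upper limit = 672 + (672 − 588)/2 = 714. Both match the SAP.

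**2. Default schedule.**

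- The Week 96 visit is on Day 672 ± 6 = 666–678.
- The follow-up is 24 to 36 days later: earliest 666 + 24 = 690, latest 678 + 36 = 714.
- Of 13 × 13 = 169 permitted date pairs, 169 lie in 631–714. In each, the follow-up is later than the Week 96 visit, so it is the record selected.
- If the first dose is taken on the date of the Day 1 visit, the SAP's plus-one rule puts the nominal visit on Day 673. The follow-up range becomes 691–715, and 168 of 169 pairs lie inside.

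**3. Sponsor-notified ±6-week visit.**

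- The visit is on Day 630–714, so the follow-up is on Day 654–750.
- Of 85 × 13 = 1,105 date pairs, 715 lie inside the window (64.7%).
- A follow-up at exactly 30 days is inside only if the visit is on or before Day 714 − 30 = 684. That is 55 of 85 possible days.

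These are counts of permitted dates, not probabilities.

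**4. Which analyses would take the value.**

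| Analysis | Limit stated | Post-drug follow-up value used? |
|---|---|---|
| Snapshot, Weeks 72 and 96 (SAP 6.2.1) | last dose + 1 day | No |
| CD4 count and CD4% (SAP 6.2.2) | last dose + 1 day | No |
| Missing=Failure, Missing=Excluded (SAP 6.2.3) | none | Yes, if drawn and in window |

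The Week 24 primary is a snapshot endpoint, and SAP 6.1.1 says it has already been analysed and will not be repeated.

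**5. Size per changed result.** With an assumed Full Analysis Set of 86, one completer crossing 50 copies/mL moves Missing=Failure by 1/86 = 1.16 points; with 80 it is 1/80 = 1.25 points. As an illustration with exact 95% intervals, 86/86 is 100% (95.8 to 100), 85/86 is 98.8% (93.7 to 100.0) and 84/86 is 97.7% (91.9 to 99.7). The documents give no basis for the number of changes.

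**The case against.** The strongest reply is that the sample may never exist. The all-visits tag is loose elsewhere too. Protocol 6.10 applies it to urine chemistry, yet Appendix 2 limits the follow-up to urinalysis. Section 6.9 applies it to plasma storage, yet both tables leave Screening blank. Protocol 9.1.6 says the eCRF captures only what the schedule requires, and two tables agree with each other. This stands as a reason to call the effect conditional. It does not settle the conflict. Chemistry and hematology carry the same tag in 6.9 and are marked at the follow-up. Section 6.9 also excludes collection after Week 96 for metabolic tests, biomarkers and inflammation markers, but not for HIV-1 RNA.

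A second reply is that off-drug values are a known feature of these methods. Protocol 1.2.3.4, describing Study GS-US-380-1490, says both analyses count values from subjects who stopped study drug but stayed in the study. That stands, and it argues against a blanket on-treatment limit. The case here differs: a completer's on-drug Week 96 value is displaced by a later one.

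Third, Missing=Failure and Missing=Excluded are SAP additions that do not appear in Protocol 8.1.3 or 8.5, and the study is single-arm and descriptive. That limits the weight of the point.

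Several stronger readings are tempting, and the documents do not support them:

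- **That the synopsis also orders the draw.** It names visits only through Week 96 before referring to all study visits.
- **That every completer's value would be replaced.** This holds only where the sample is drawn, and nearly always only on the default schedule.
- **That off study drug means off therapy.** Care passes to the treating physician (Protocol 6.8), and Protocol 1.7 says all patients should receive effective treatment.
- **That 6.12.2 distorts a planned analysis.** The SAP has no virologic-failure endpoint; the wording bears on classification and resistance testing.

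**Conclusion.** The conflict between Protocol 6.4.2/6.9 and the two procedures tables is real, and the SAP does not guard against its consequence. If the sample is drawn on the default schedule, it falls inside the Week 96 window in all 169 permitted date pairs (168 under the alternative day count) and becomes the Week 96 value in two SAP secondary analyses. With a ±6-week visit, about 65% of permitted date pairs do so.

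The conclusion rests on three assumptions: the draw takes place, the last dose is at the Week 96 visit, and SAP 3.8.3 is applied as written. A reader might infer that the main efficacy result is in doubt; it is not, because the last-dose-plus-one-day limit protects the snapshot. A reader might also infer a shift of several points, but only the size of each change can be stated. This is a modest defect, worth correcting because the remedy is almost free.

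**What to change.** In SAP 3.8.3 (or 6.2.3) add: *HIV-1 RNA collected at the 30-Day Follow-Up visit is listed but not assigned to an analysis window.* This works whichever schedule the sponsor keeps. It leaves in the analysis the scheduled-visit values of subjects who stopped study drug but continued to attend.

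Separately, the sponsor should reconcile two pairs of passages: Protocol 6.4.2 and 6.9 with Appendix 2 and SAP Appendix 1 on HIV-1 RNA and CD4 at the follow-up, and the last-visit wording of Protocol 6.12.2 with the definition in 6.12. Which rule to keep is for the sponsor to decide. The synopsis needs no change.

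The cost is one SAP sentence and two textual reconciliations, with no new data. The downside is negligible: any follow-up values would appear only in listings.
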